4.2 Withdrawal from the Study, Discontinuation of Study Product, or Study Termination

4.2.1 Withdrawal from the Study or Discontinuation of the Study Product

Subjects may voluntarily withdraw their consent for study participation at any time without penalty or loss of benefits to which they are otherwise entitled.

An investigator may also discontinue a subject from receiving study product for any reason. Follow-up safety evaluations will be conducted if the subject agrees. If a subject discontinues

study product or is withdrawn from the study prior to completion, the reason for this decision must be recorded in the eCRFs.

The reasons for withdrawal or discontinuation of study product, might include, but are not limited to the following:

- Subject meets halting criteria
- Subject becomes noncompliant
- Disease or medical condition, or new clinical finding(s) for which continued participation, in the opinion of the investigator might compromise the safety of the subject, interfere with the subject's successful completion of this study, or interfere with the evaluation of responses
- Subject becomes lost to follow-up
- Subject becomes pregnant

The investigator should be explicit regarding study follow-up (e.g., safety follow-up) that might be carried out despite the fact the subject will not receive further study product. The alternate visit schedule and procedures pertaining to subjects withdrawn from study product will be further explained in the MOP. If the subject agrees, every attempt will be made to follow all AEs through resolution or stabilization.

The procedures that collect safety data for the purposes of research must be inclusive in the original informed consent or the investigator may seek subsequent informed consent using an IRB/IEC approved consent form with the revised procedures.

Investigator will inform the subject that already collected data will be retained and analyzed even if the subject withdraws or is discontinued from this study.

4.2.2 Handling of Withdrawals

In the case of subjects who are lost to follow-up, extensive effort (i.e., three documented contact attempts via phone calls, emails, text messages, etc., made on separate occasions and followed by a certified letter) will be made to locate or recall them, or at least to determine their health status. These efforts will be documented in the subject's study records. Every attempt will be made to follow all AEs, including solicited local site and systemic AEs, unsolicited non-serious AEs, and SAEs, ongoing at the time of early withdrawal through resolution or stabilization as per applicable collection times defined for the specific type of AE.

Subjects who withdraw, or are withdrawn from this study, or are lost to follow-up after signing the informed consent form (ICF) and administration of the study product will not be replaced. Subjects who withdraw, or are withdrawn from this study, or are lost to follow-up after signing the ICF but before administration of the study product may be replaced.

4.2.3 Study Termination

If the study is prematurely terminated by the sponsor, any regulatory authority, or the investigator for any reason, the investigator will promptly inform the study subjects and assure appropriate therapy or follow-up for the subjects, as necessary. The investigator will provide a detailed written explanation of the termination to the IRB/IEC.

5 STUDY PROCEDURES

Study Duration

It is projected that the length of the overall study, from initiating screening to the completion of the last safety communication follow up visit, will be approximately 24 months. This projection is based on the six sentinel subjects in each cohort and the assumption that vaccination of the next cohort will begin after the SRC has reviewed blinded safety data through the reactogenicity period post-3rd study vaccination in the previous cohort. Additionally, as the study is using a novel adjuvant, study participants will receive a final safety call approximately 1 year after receiving their final vaccination to assess for new onset AEs of special interest.

Duration of Individual Subject Participation

Participation for an individual subject will be approximately 15 months, which includes a 30-day screening period, vaccination at Day 1, 29, and 57, and active surveillance through 28 days after the 3rd dose of vaccine. Safety communication contacts will be made at 6 months and 1 year post final vaccination.

Study Schedule

Complete study schedule details listed by type of visit are described below. Refer also to [Appendix A. Schedule of Events](#).

5.1 Screening

Day -30 to -2

The following activities will be performed at screening and may be done all at one visit or split into separate visits.

- Subjects will be provided with a description of this trial (purpose and study procedures) and asked to read and sign the ICF. The ICF will be signed prior to performing any study procedures, including any screening procedures.
- Demographic information will be obtained by interview of subjects.
- Eligibility criteria will be reviewed with subjects.

The following screening procedures will be completed to ensure that the potential subject is eligible for the study:

- Complete medical history will be obtained by interview of subjects, including current contraceptive history with females of childbearing potential and receipt of seasonal influenza and COVID-19 vaccines for all participants.
- History of all concomitant medications taken within 30 days prior to signing the ICF will be obtained by interview of subjects or abstraction from eCRF.
- Vital signs, including oral temperature, pulse, and BP, will be obtained. Subjects must not eat or drink anything hot or cold, or smoke within 10 minutes prior to taking oral temperature.
- Height and weight will be collected for BMI calculation.
- An abbreviated physical examination will be performed to include the following organs and organ systems: general appearance, skin, head and neck, lungs, heart, liver, spleen, extremities, musculoskeletal and lymph nodes by a study clinician licensed to make medical diagnoses and listed on the Form FDA 1572 as the site PI or sub-investigator. Breast, genito-urinary and rectal exams are not considered a routine part of the abbreviated physical exam.
- A urine pregnancy test will be performed on all females of childbearing potential and must be negative.
- Counsel on avoidance of pregnancy for females of childbearing potential.
- A urine dipstick will be performed for urine protein.
- A urine toxicology will be performed for opiates.
- A stool kit and collection instructions will be provided in anticipating for the expected sample at enrollment.
- Venous blood will be collected for screening laboratory tests. These include:
 - Hematology: WBC, absolute neutrophil count (ANC) hemoglobin (Hgb), and platelets (PLTs)
 - Chemistry: total bilirubin (T. bili), alanine aminotransferase (ALT), creatinine, sodium, potassium
 - Serology: HIV – 1/2 antibody, HCV, HBsAg, HLA-B27

Testing results must be confirmed to meet the eligibility criteria as outlined in the Inclusion / Exclusion Criteria prior to randomization. Acceptable screening laboratory values are those that fall within the normal ranges as listed in [Appendix B](#).

- A low creatinine value or a low ALT value, as well as trace amounts of urinary protein, are acceptable for study inclusion.
- As they are not considered to be clinically significant, subjects with a Grade 1 abnormality may be re-screened once if there is a suspected inter-current, short-term medical illness or a suspected laboratory error.

If screening labs are collected more than 30 days before vaccination, the screening labs may be re-collected to determine if the subject remains eligible for study participation. No subject may be screened **more than twice due to a screening failure result as defined above**. The Study Sponsor and PI will be contacted for clarification or questions regarding screening failures. All eligibility criteria must be satisfied before a subject is enrolled.

A subject may also be re-screened if the subject was screened eligible for a previous cohort but was not enrolled (e.g., scheduling conflict, vacation).

Subjects will be informed of their screening test results by a member of the study team. Subjects will be encouraged to follow up with their primary care providers if results are of clinical significance or are sensitive in nature.

5.2 Enrollment/Baseline

Day 1, Visit 01

Subjects who pass screening and meet all the inclusion criteria and none of the exclusion criteria may be considered for study enrollment.

- Screening blood testing and study entry requirements will be reviewed with subjects prior to the first study vaccination to ensure subjects continue to qualify for vaccination. Laboratory results must be within acceptable parameters as outlined in the inclusion / exclusion criteria.
- Interim medical history, including an assessment for new medical conditions, stability of chronic diseases, MAAEs, NOCMCs and symptoms suggestive of PIMMCs, will be obtained by interview of subjects prior to study vaccination. Any changes in medical

history since the screening visit will be reviewed to ensure subjects continue to qualify for vaccination.

- All concomitant medications will be reviewed with subjects prior to study vaccination for accuracy and completeness. Any new concomitant medications will be reviewed to ensure subjects continue to qualify for vaccination.
- Vital signs, including oral temperature, pulse, and BP, will be obtained prior to study vaccination to ensure subjects continue to qualify for vaccination. Vital signs assessed on Day 1 prior to study vaccination will be considered as baseline. Subjects must not eat or drink anything hot or cold, or smoke within 10 minutes prior to taking oral temperature.
- If indicated, a targeted physical examination may be performed prior to study vaccination.
- For all participants of childbearing potential, a urine pregnancy test will be performed within 24 hours of vaccination. Results must be negative and known prior to study vaccination.
- Pre-vaccination Reactogenicity assessments will be completed.
- Venous blood will be collected immediately prior to study vaccination for:
 - Serum for Serology
 - PBMC for ALS
 - PBMC for secondary research
 - Serum for secondary research
- Attempt to collect stool sample for future use. Every attempt should be made to collect sample from participant. Enrollment can continue in the rare case the sample cannot be collected.
- Subjects will be enrolled in Advantage eClinical® and randomly assigned to a treatment arm prior to study vaccination.
- Subjects will receive one dose of study vaccine via a single IM injection into the deltoid muscle of the subject's arm. It is strongly recommended the unblinded administrator administers the study product(s) into the subject's left deltoid. The site of injection and time of study vaccine administration to the subject will be recorded on the appropriate eCRF
- Subjects will be observed in the clinic for at least 30 minutes after study vaccination. The study vaccination site will be examined, post-administration reactogenicity assessments

will be performed, and any AE/SAEs will be recorded on the appropriate eCRF prior to discharge from the clinic.

- Subjects will be instructed how to complete their e-memory aid. Subjects will be provided with study-related materials (including a digital thermometer and measuring ruler) to record daily oral temperature and potential solicited injection site reactions. Subjects will be encouraged to take their oral temperature around the same time each day. Subjects must not eat or drink anything hot or cold, or smoke within 10 minutes prior to taking oral temperature. Subjects will be instructed to notify the study center if they develop any severe reactions after study vaccination. If the site PI or appropriate sub-investigator deems the reaction severe enough, further instructions will be given to the subject on the proper course of action, including a return to the clinic for immediate evaluation if appropriate.
- Counsel on avoidance of pregnancy for females of childbearing potential.

5.3 Follow up Visits

Follow-up visits are scheduled in reference to most recent study vaccination date. See [Appendix A](#). Schedule of Events.

5.3.1 Follow up: 3 Days (± 1) and 15 Days (± 2) following each vaccine

These visits may be performed in the clinic or virtually.

The following procedures as applicable, will occur.

- Interim medical history, including an assessment for new medical conditions, stability of chronic diseases, MAAEs, NOCMCs, and PIMMCs, will be obtained by interview of subjects and any changes since the previous visit will be noted.
- All concomitant medications will be reviewed with subjects and recorded on the appropriate eCRF.
- Vital signs, including oral temperature, pulse, and BP, will be obtained. Subjects must not eat or drink anything hot or cold, or smoke within 10 minutes prior to taking oral temperature.
- A targeted physical examination may be performed if indicated based on review of complete medical history and any updates obtained by interview of subjects since the previous visit, by a study clinician licensed to make medical diagnoses and listed on the Form FDA 1572 as the site PI or sub-investigator.

- All AE/SAEs will be recorded on the appropriate eCRF.
- The study vaccination site will be examined, except for visits 04, 08, and 12.
- E-Memory Aid information will be reviewed with subjects, except for visits 04, 08, and 12.
- Counsel on avoidance of pregnancy for females of childbearing potential.
- A stool kit and collection instructions will be provided in anticipation for the expected sample at the next visit, except for visits 04, 08 and 12.

5.3.2 Follow up: 7 Days (+1) after each vaccination

All procedures listed in [section 5.3.1](#) as well as procedures listed below are to be performed unless exceptions are noted.

- Venous blood will be collected for:
 - WBC, Hgb, PLT, ANC, ALT, T. bili, creatinine, sodium, and potassium.
 - Serum for Serology
 - PBMC for ALS
 - PBMC for secondary research
 - Serum for secondary research
- E-Memory Aid information will be reviewed with subjects
- Attempt to collect stool sample.

5.3.3 Subsequent Vaccination Visits: Day 29 (+2) and Day 57 (+2)

All subjects in each cohort will return on Day 29 (Visit 05) and Day 57 (Visit 09) after vaccination 1 and undergo the following procedures:

- Qualification criteria for subsequent vaccination visits, will be reviewed prior to vaccination. [Section 4.1.3](#)
- Interim medical history, including an assessment for new medical conditions, stability of chronic diseases, MAAEs, NOCMCs and symptoms suggestive of PIMMCs, will be obtained by interview of subjects prior to study vaccination. Any changes in medical history since the screening visit will be reviewed to ensure subjects continue to qualify for vaccination.

- Concomitant medications will be reviewed with subjects prior to study vaccination for accuracy and completeness. Any new concomitant medications will be reviewed to ensure subjects continue to qualify for vaccination.
- Vital signs, including oral temperature, pulse, and BP, will be obtained prior to study vaccination to ensure subjects continue to qualify for vaccination. Subjects must not eat or drink anything hot or cold, or smoke within 10 minutes prior to taking oral temperature.
- If indicated after review of subject history, a targeted physical examination may be performed prior to study vaccination.
- For all participants of childbearing potential, a urine pregnancy test will be performed within 24 hours of vaccination. Results must be negative and known prior to study vaccination.
- Pre-vaccination reactogenicity assessments will be completed
- Venous blood will be collected immediately prior to study vaccination for:
 - Serum for Serology
 - PBMC for secondary research
 - Serum for secondary research
- Subjects will receive one dose of study vaccine via a single IM injection into the deltoid muscle of the subject's arm. It is strongly recommended the unblinded administrator alternate the subject's arms for injections. The site of injection (right or left arm) and time of study vaccine administration to the subject will be recorded on the appropriate eCRF.
- Subjects will be observed in the clinic for at least 30 minutes after study vaccination. The study vaccination site will be examined, post-administration reactogenicity assessments will be performed, and any AE/SAEs will be recorded on the appropriate eCRF prior to discharge from the clinic.
- Subjects will be instructed how to complete their e-memory aid. Subjects will be provided with study-related materials to record daily oral temperature and potential solicited injection site reactions. Subjects will be encouraged to take their oral temperature around the same time each day. Subjects must not eat or drink anything hot or cold, or smoke within 10 minutes prior to taking oral temperature. Subjects will be instructed to notify the study center if they develop any severe reactions after study vaccination. If the site PI or appropriate sub-investigator deems the reaction severe

enough, further instructions will be given to the subject on the proper course of action, including a return to the clinic for immediate evaluation if appropriate.

- Counsel on avoidance of pregnancy for females of childbearing potential.

5.3.4 Follow-up: Day 85 (± 2) and Day 113 (± 4)

All cohorts will return on Day 85 (Visit 13) and 113 (visit 14). The following procedures will be performed.

- Interim medical history, including an assessment for new medical conditions, stability of chronic diseases and symptoms, MAAEs, NOCMCs, and suggestive of PIMMCs, will be obtained by interview of subjects. Please note that AEs (new medical conditions) will be assessed for 28 days post last vaccination. SAEs will be followed throughout the study duration.
- Concomitant medications will be reviewed with subjects for accuracy and completeness. Only concomitant medications taken within 30 days of enrollment through 28 days post last vaccination are collected in Advantage eClinical®.
- Vital signs, including oral temperature, pulse, and BP, will be obtained. Subjects must not eat or drink anything hot or cold, or smoke within 10 minutes prior to taking oral temperature.
- If indicated after review of subject history, a targeted physical examination may be performed.
- For all participants of childbearing potential, a urine pregnancy test will be performed.
- Counsel on avoidance of pregnancy for females of childbearing potential.
- Venous blood will be collected for:
 - Serum for Serology
 - PBMC for secondary research
 - Serum for secondary research

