3 STUDY INTERVENTION/INVESTIGATIONAL PRODUCT

3.1 Study Product Description

3.1.1 CJCV2

The vaccine to be evaluated in the current project is a *C. jejuni* CCV named CJCV2 produced from an engineered mutant of 81-176 that is lacking an enzyme responsible for the production of a LOS that could potentially trigger GBS. In contrast to the strain used for CJCV1 (which was made from strain 3208), a natural variant of 3208 (named 3208.1) was selected that presents the two *O*-methyl phosphoramidate (MeOPN) transferases in the "on" status to ensure that there is an optimum amount of MeOPN on the capsule. The CPS is conjugated to CRM₁₉₇, a non-toxic mutant protein of diphtheria toxin at a CPS: CRM₁₉₇ ratio of 2:1. The CJCV2 vaccine product was manufactured at Inventprise LLC (Redmond, Washington) with final fill and finish completed by The University of Iowa Pharmaceuticals (Iowa City, Iowa), both performed under current Good Manufacturing Practices (cGMP) conditions.

- **Role of this study in clinical development**

This will be a Phase 1, first-in-human study of CJCV2 (1, 3, or 10 µg), with or without a fixed dose of ALFQ (200 µg 3D-PHAD® and 100 µg QS-21) to evaluate the safety and immunogenicity of the vaccine. A successful study will provide data for an increased number of subjects to receive an optimal CJCV2 dose (with or without adjuvant), and to potentially evaluate vaccine efficacy in a controlled human infection model (CHIM) with *C. jejuni* strain CG8421.

- **Prior studies of the study product**

Under US Army sponsorship, the Naval Medical Research Center (NMRC) recently completed a Phase 1, first-in-human trial with the prototype *C. jejuni* CPS vaccine conjugated to CRM₁₉₇, called CJCV1 (ClinicalTrials.gov Identifier: NCT02067676). The vaccine was manufactured using NIAID funding (NIH U01 AI082105) and delivered intramuscularly with AH. Forty-eight subjects (eight per group) received two doses of 2, 5, or 10 µg of the CJCV1 intramuscularly with or without 125 µg of AH on Days 0 and 28. There were no vaccine-related SAEs or unanticipated events. The vaccine was well-tolerated, with all vaccine-related AEs being mild to moderate vaccine site pain or tenderness. Irrespective of the CJCV1 dose delivered, only 6 of 48 subjects (12.5%) seroconverted against the CPS.

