6. Participation in a previous *Campylobacter* study or reports having received vaccination against *Campylobacter* within the last 3 years.
7. History of microbiologically confirmed *Campylobacter* infection in the last 3 years.
8. Occupation involving handling of *Campylobacter* bacteria or vaccine products currently or in the past 3 years.
9. Use of immunosuppressive/immunomodulating disease therapy within 90 days
10. Received Ig or other blood products (with exception of Rho D Ig) within 90 days prior to enrollment.
11. Have a history of severe reactions following previous immunization with any licensed or unlicensed vaccine.
12. Known hypersensitivity to any components of vaccine, adjuvant, or diluent.
13. Received or plan to receive a licensed live vaccine within 30 days prior to 1st vaccination and to 30 days after the last vaccination.
14. Received or plan to receive a licensed, inactivated, vaccine within 14 days prior to 1st vaccination to 14 days after the last vaccination, or a seasonal influenza and/or COVID-19 vaccine \pm 7 days from study product vaccination.
15. Individuals in whom the ability to observe possible local reactions at the eligible injection sites (deltoid region) is unacceptably obscured due to a physical condition or permanent body art.
16. Within 14 days prior to vaccination has received an oral or parenteral (including intra-articular) corticosteroid of any dose for 5 or more days, or high-dose inhaled corticosteroids.
 - a. High dose defined per age as using inhaled high dose per reference chart (https://www.nhlbi.nih.gov/files/docs/guidelines/asthma_qrg.pdf)
17. Current or history of alcohol or drug abuse within one year prior to enrollment.

18. Have any diagnosis, current or past, of schizophrenia, bipolar disease, or other psychiatric diagnosis that may interfere with subject compliance or safety evaluations.
19. Have been hospitalized for psychiatric illness, history of suicide attempt, or confinement for danger to self or others within one year prior to enrollment.
20. Are pregnant, breastfeeding, or plan to become pregnant or breastfeed at any given time during the study.
21. Have an acute illness as determined by study clinician licensed to make medical diagnoses and listed on the Form FDA 1572 as the site PI or sub-investigator, within 72 hours prior to enrollment.

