6.1.2 Assessment of Concomitant Medications/Treatments other than Study Product

- Administration of any medications or non-study vaccines will be documented in the appropriate eCRF. All concomitant medications, taken in the 30 days prior to study enrollment through 28 days following last vaccination or early termination, whichever occurs first, will be recorded. All concomitant medications associated with SAEs, MAAEs, NOCMCs, and PIMMCs through the assessment period for these events will be recorded.
- All prescription and over-the-counter medications as well as vitamins and supplements will be recorded.

Assessment of eligibility also will include a review of permitted and prohibited medications (per the exclusion criteria).

Use of new medications should prompt evaluation for the presence of an AE or new chronic medical condition.

Medications which may interfere with the evaluation of the investigational product should not be used unless absolutely necessary. Medications or treatments which are prohibited are listed in the exclusion criteria.

6.1.3 Assessment of Subject Compliance with Study Intervention/Investigational Product/Investigational Device

Subjects will be directly observed at the time of dosing by a member of the clinical research team who is delegated to administer the study product. Administration will be documented in the appropriate eCRF.

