#### 6.3.3. Per Protocol Immunogenicity Population

The Per Protocol (PP) Immunogenicity Population includes all participants in the Full Immunogenicity Population with the following exclusions:

- Data from all available visits for participants found to be ineligible at baseline.
- Data from all visits after major protocol deviations, such as:
  - Receipt of an incorrect study vaccination.
  - Second or third vaccination not received.
  - Second or third vaccination received out of window.
  - Receipt of any of the following:

- Licensed, live vaccine within 30 days of any vaccination.
- Licensed, inactivated vaccine within 14 days of any vaccination.
- Investigational products at any time during study period.
- Data from any visit that occurs out of window.

All protocol deviations will undergo a review prior to database lock, blinded to outcome value to determine if the affected visit and any subsequent visits will be excluded from the PP Immunogenicity Population for the affected participant(s).

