#### 9.1.2. Prior and Concomitant Medications

Medications (prescription and over-the counter) and non-study vaccinations taken 30 days prior to enrollment through 28 days after the final vaccination or early termination, whichever occurs first, will be classified using the World Health Organization (WHO) Drug Dictionary (March 2024) Anatomical Therapeutic Chemical (ATC) Classification Levels 1 and 2 and summarized by treatment group and overall ([Table 98](#)).

Individual participant listings of all prior and concomitant medications will be presented ([Listing 16](#)).

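### Non-study vaccines are not systematically recorded after about Day 85 and, once permitted, trigger no exclusion, so exploratory anti-CRM197 titers at Day 85, Day 113 and peak can be raised by another vaccine

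*Protocol*

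**What the plan says.** **Recording.** Protocol 5.3.4, which governs the Day 85 and Day 113 visits, limits data entry: "Only concomitant medications taken within 30 days of enrollment through 28 days post last vaccination are collected in Advantage eClinical". Protocol 6.1.2, Appendix A note c and SAP 4.4.7 give the same 28-day limit for concomitant medications. SAP 9.1.2 classifies and summarises medications together with "non-study vaccinations taken 30 days prior to enrollment through 28 days after the final vaccination or early termination". There is one stated exception, in protocol 6.1.2: "All concomitant medications associated with SAEs, MAAEs, NOCMCs, and PIMMCs through the assessment period for these events will be recorded".

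**Titers.** Serum IgG and IgM against capsule and CRM197 are analysed at Days 8, 29, 36, 57, 64, 85 and 113 (SAP 3.2). SAP 3.3 defines peak titer and peak fold-rise over all times after the first dose, so Day 113 is included. The dose correlations in SAP 11.4 take the serum maximum over Days 64, 85 and 113 for the third vaccination.

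**Permitted vaccines.** Protocol 4.1.2 bars anyone who has "Received or plan to receive a licensed, inactivated, vaccine within 14 days prior to 1st vaccination to 14 days after the last vaccination". Live vaccines are barred to 30 days after the last dose.

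**Per-protocol rule.** SAP 6.3.3 lists as examples of major deviations "Licensed, live vaccine within 30 days of any vaccination", an inactivated vaccine within 14 days, and "Investigational products at any time during study period".

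**Carrier.** Protocol 3.1.1 describes CRM197 as "a non-toxic mutant protein of diphtheria toxin".

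**The concern.** The record of outside exposures ends four weeks before the last titer that depends on it. After the two vaccine restrictions lapse, an ordinary licensed vaccine breaks no rule, so it does not enter the deviation log. After about Day 85 it has no routine place in the medication data either. Between about Day 72 and Day 85 it would be recorded, but nothing in SAP 6.3.3 acts on it, because the inactivated-vaccine window is only 14 days.

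This matters for one set of endpoints. The trial measures anti-CRM197 IgG and IgM and reads a rise as a response to CJCV2. CRM197 derives from diphtheria toxin, so a routine vaccine containing diphtheria toxoid or a CRM197 conjugate is a plausible competing cause of a rise. Such a rise would enter the GMT, fold-rise and responder rate at the affected visit, and the participant's peak. The report would then have no systematic record with which to explain it, and no rule for removing it.

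**Working it through.** **Inputs.** Doses on Days 1, 29 and 57; recording to 28 days after the last dose; inactivated-vaccine restriction of 14 days and live-vaccine restriction of 30 days after the last dose; last serum on Day 113 (±4); 10 participants per group.

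**Calendar.** The SAP's own labels reproduce: 57 + 28 = Day 85 and 57 + 56 = Day 113.

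- Recording ends: 57 + 28 = Day 85.
- Unrecorded days before the last titer: 113 − 85 = 28, or 24 to 32 with the ±4 window (109 − 85; 117 − 85). As a share of serology follow-up after dose 3: 28/56 = 50%.
- Inactivated-vaccine restriction ends: 57 + 14 = Day 71, so such vaccines are permitted from Day 72. Permitted and recorded but not excluded: Days 72-85, 14 days. Permitted and not systematically recorded: Days 86-113, 28 days.
- Live-vaccine restriction ends: 57 + 30 = Day 87, so permitted from Day 88. Permitted and not systematically recorded: Days 88-113, 26 days.
- Prohibited but past the medication cut-off: live vaccine on Days 86-87, 2 days; inactivated vaccine, 0 days; investigational product, 28 days up to the last titer.
- If dose 2 was the last dose: recording ends at 29 + 28 = Day 57, and the gap to Day 113 is 56 days. SAP 6.3.3 removes visits after a missed third dose from the per-protocol set, so this longer gap affects the Full Immunogenicity Population.

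**Visits touched.** Of seven post-baseline serum visits, Day 113 lies wholly after the cut-off. Day 85 is reached by a vaccine given on Days 72-85. The ALS visits (Days 8, 36, 64) all precede Day 72, so none is touched.

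**Size of one event.** If one of 10 titers is multiplied by k, the group GMT is multiplied by k^(1/10). The values of k are assumptions.

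- k = 4: 4^(1/10) = 1.149, a rise of 15%.
- k = 10: 10^(1/10) = 1.259, a rise of 26%.
- Responder rate: at most 1/10 = 10 percentage points, and only if that participant was not already at a 4-fold rise.
- Peak: changes only if the boosted value exceeds every earlier titer.

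**Chance of an event.** The documents give no rate. For an assumed probability q of a relevant exposure over the 28 days, the chance of at least one among n is 1 − (1 − q)^n.

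| q | n = 10 | n = 60 |
|---|---|---|
| 1% | 10% | 45% |
| 5% | 40% | 95% |
| 10% | 65% | 99.8% |

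These are illustrations. For vaccines containing diphtheria toxoid or CRM197 alone, the true rate could lie below this range.

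**The case against.** Several safeguards exist, and most of them stand.

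- **Deviation route.** The per-protocol vaccine and investigational-product items are examples of major deviations. Protocol 5.5 requires all deviations to be addressed in eCRFs, with no 28-day limit, and SAP 6.3.3 has them reviewed before lock. A reader might infer that the per-protocol exclusions cannot be applied after Day 85. The documents do not support that: an investigational product, or a live vaccine on Days 86-87, is prohibited and can be captured this way. The route does not reach a permitted vaccine.
- **Review at Day 113.** Protocol 5.3.4 says "Concomitant medications will be reviewed with subjects for accuracy and completeness", and SAP Table 2 marks a medication review at Visit 14. A later exposure might therefore be heard of, so calling it invisible would go too far. But the next sentence of 5.3.4 restricts what is collected, and protocol Appendix A shows no such review at Visit 14. The opening sentence of 6.1.2 asks for non-study vaccines to be documented without its own end date; SAP 9.1.2 still summarises them only to 28 days.
- **Drugs.** A reader might also infer that later immunosuppressants or steroids go unrecorded. A drug associated with a medically attended event is recorded throughout follow-up, and the per-protocol rule lists no medications. A preventive vaccination is not an adverse event, so the exception does not help there.
- **Outliers.** SAP 6.5 provides sensitivity analyses for inexplicable values, and Tables 25-26 show how many maxima fall at Day 113. These help, but a high titer in a vaccinated participant need not look inexplicable.
- **Design.** The trial is descriptive, randomized and blinded, so outside vaccines should not systematically favour either arm. That stands. It does not protect absolute titers, or rule out chance imbalance, with 10 per group.

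**Conclusion.** The point holds in a narrow form. Routine recording stops 28 days before the last serum titer (56 days if only two doses were given). Permitted licensed vaccines fall outside both the deviation log and the per-protocol rule, whether recorded or not. The endpoints exposed are the exploratory anti-CRM197 IgG and IgM results at Day 85, Day 113 and peak, and the SAP 11.4 correlations that use those maxima.

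The cross-effect on anti-CRM197 titers is an inference from the protocol's description of the carrier; the documents do not state it. A reader might extend it to the secondary endpoint, capsule-specific IgG. The documents name no non-study vaccine that would alter that titer, so the extension is unsupported.

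Per event the effect is modest: about 15% on a group GMT for an assumed 4-fold boost, and at most 10 points on a responder rate. For scale, the plan's own exact interval for 0 of 10 runs to 1 − 0.025^(1/10) = 31%. How often it would happen is unknown. This is a cheap improvement that closes a real path for bias in exploratory results. It does not threaten the primary or secondary conclusions.

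**What to change.** 1. **Collection.** In protocol 5.3.4, 6.1.2 and Appendix A note c, and in SAP 4.4.7 and 9.1.2, extend eCRF recording of non-study vaccines, investigational products, and immunoglobulin or blood products through the Day 113 visit.
2. **Consistency.** Align the Visit 14 medication review in protocol Appendix A with protocol 5.3.4 and SAP Table 2.
3. **Analysis rule.** Longer recording alone changes nothing, because no rule acts on a permitted vaccine. In SAP 6.3.3, exclude from the per-protocol CRM197 IgG and IgM analyses any visit after receipt, on or after Day 1, of a vaccine containing diphtheria toxoid or CRM197. Alternatively, make that exclusion a named sensitivity analysis.
4. **Where collection is complete.** The SAP says Cohort 1 has finished follow-up and Cohorts 2 and 3 have been enrolled, so step 1 may come too late for some or all participants. In that case footnote Tables 17, 18, 23 and 24 to say that exposures from Day 85 to Day 113 were not systematically recorded, and show CRM197 peak titer with and without Day 113. The ALS tables (19 and 20) need no note.

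The cost is a few eCRF lines at a clinic visit that already takes an interim history, one SAP sentence, and possibly a few more per-protocol visit exclusions. The fallback in step 4 needs no new data.
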